## 6.3 Planned Study Visits

### 6.3.1 Visit 2 (Day 29 [Window: Days 29-35]) Follow-up

- Medical history will be reviewed and updated as appropriate.
- Interim sexual history since the last clinic visit will be collected.
- Vaginal symptoms will be assessed.
- A urine pregnancy test will be performed on all participants of childbearing potential.
- Compliance with the study protocol criteria will be assessed; all used and unused study IP packaging will be collected as relevant and recorded.
- Participant memory aid will be collected and reviewed.
- All concomitant medications taken since V1 will be recorded on the appropriate DCF. Previously recorded medications will be updated as appropriate.
- Study personnel will discuss with participants and assess and record all AE/SAEs. Previously recorded AE/SAEs will be updated as appropriate.
- If clinically indicated, a targeted physical examination will be performed by a qualified study clinician.
- A pelvic examination to include examination of external genitalia will be conducted, and swabs and samples taken for analysis of Amsel criteria; KOH and saline microscopy for identification of yeast forms, trichomonas, and clue cells; Gram staining; the BD Max test; and for future analysis, for participants who consented to future use of their specimens. Instructions for obtaining vaginal swab specimens for these assessments are outlined in the

---

protocol specific MOP. Gram stain Nugent scoring will be conducted in the Central Laboratory; all other testing will be conducted locally.

- Participants with clinical evidence of VVC based on vulvovaginal signs (edema, erythema, and/or excoriation) and symptoms (vulvovaginal itching, burning, and/or irritation) will have a confirmatory vaginal *Candida* culture and treated as appropriate with oral fluconazole. Participants who cannot take oral fluconazole will be terminated from the study.
- Vulvovaginal signs will be assessed and graded by severity, as applicable.
- A clinical determination for BV recurrence will be made based on evaluation of Amsel criteria. The presence of >2 of 4 Amsel criteria is required for a diagnosis of BV recurrence. Participants with a clinical diagnosis of BV recurrence will complete a satisfaction questionnaire and will be terminated from the study.

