### **7.1.2      Assessment of Participant Compliance with Study Intervention/Investigational Product**

The TOL-463 Insert and placebo are inserted by the study participant.

At each follow up visit, V2 through V4, participants will be asked to bring the study IP packaging, unused inserts (if any) and memory aid corresponding to the return visit (V2, V3 or V4) to the study personnel. Study personnel will review adherence to the study IP schedule with the participants, including the participant memory aid, and record this on the appropriate DCF at each follow-up visit and any unscheduled visits. Study personnel will record the number of unused inserts and empty packaging returned at each of the follow-up visits, V2 thru V4.

Compliance with the study protocol will be assessed and documented by study personnel at each of the follow-up visits, V2 thru V4, and at any unscheduled visits. Study personnel may discard the participant's memory aid after documenting compliance. Refer to 4.4 for instructions on handling of returned study IP packaging.

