#### **10.5.4.2 Secondary Efficacy Analyses**

The secondary efficacy analyses are briefly described below. Secondary efficacy analyses will be performed in the mITT and PP analysis populations, where appropriate. Details of these analyses and any sensitivity analyses will be specified in the separate SAP document.

For the analysis of Secondary Objective 1, the median time to BV recurrence will be estimated by treatment group using Kaplan-Meier estimates. For participants who experience BV recurrence by V4, the time of BV recurrence will be defined as the midpoint between the earliest time point of a positive BV diagnosis (post-baseline) and the previous observed time-point. For participants without BV recurrence at or before V4, the BV recurrence endpoint will be coded as censored, with time to recurrence defined as the elapsed time from the first dose of IP, to the earliest of: V4 time-point, the last observed time-point prior to loss to follow-up, or the time-point at which the participant became ineligible for the particular analysis population.

For the analysis of Secondary Objective 2, the proportion of participants experiencing vaginal symptoms as assessed by the participant via the daily memory aid will be estimated overall, by symptom category, and by treatment group.

For the analysis of Secondary Objective 3, responses to the satisfaction questionnaire will be summarized overall and by treatment group. Categorical responses will be summarized using contingency tables and/or odds ratios, while continuous responses will be summarized using measures of central tendency such as the mean or median, and measures of dispersion such as the standard deviation or interquartile range.

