3.2.2. Secondary Endpoints

1. Time to BV recurrence.
2. Proportion of participants reporting BV symptoms through the follow-up period.
3. Number of participants satisfied with the study treatment through the follow-up period.
4. The occurrence of AEs considered product-related following initiation of study treatment and through the final study visit.

5. The occurrence of culture confirmed secondary VVC following initiation of study treatment and through the final study visit.

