For the analysis of Secondary Objective 1, the time to BV recurrence will be estimated by treatment group using Kaplan-Meier estimates. For participants who experience clinically diagnosed BV recurrence in study by V4, the time of BV recurrence will be defined as the midpoint between the earliest time point of a positive BV diagnosis (post-baseline) and the previous observed time-point. Subjects with BV recurrence diagnosed off study will be treated as missing time to BV recurrence and excluded from the analyses for secondary endpoints, as defined above and in Section 6.5. For participants without BV recurrence at or before V4, the BV recurrence endpoint will be coded as censored, with time to recurrence defined as the elapsed time from the first dose of IP, to the earliest of: V4 time-point, the last observed time-point prior to loss to follow-up, or the time-point at which the participant became ineligible for the particular analysis population.

For the analysis of Secondary Objective 2, the proportion of participants experiencing BV symptoms will be estimated overall, by symptom category, and by treatment group.

For the analysis of Secondary Objective 3, responses to the satisfaction questionnaire will be summarized overall and by treatment group. Categorical responses will be summarized using contingency tables.

Descriptions of the analyses to assess the exploratory objective as well as other analyses that will support the primary and secondary efficacy analyses will be provided in Section 8.4.

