The pseudocode to fit the above analyses is below:

```
proc lifetest method=KM plots=survival(cb=hw test=atrisk) data=dataset outs=surv;
  strata treatment / test=logrank;
  Time time*censor(censored_value);
run;
```

For the Secondary Objective 2, the proportion of participants experiencing vaginal symptoms will be estimated overall, by symptom category, and by treatment group at each visit. See [Table 15](#) for mITT population and [Table 16](#) for PP population. A subject listing of BV symptoms will be presented ([Listing 8](#))

For the Secondary Objective 3, responses to the satisfaction questionnaire will be summarized overall and by treatment group. See [Table 17](#) for mITT population and [Table 18](#) for PP population. Individual subject listings will be presented for all responses to satisfaction questionnaire ([Listing 9](#)).

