14. TECHNICAL DETAILS

SAS version 9.4 or above will be used to generate all TFL.

**15. SUMMARY OF CHANGES IN THE CONDUCT OF THE STUDY OR
PLANNED ANALYSES**

The analyses described in this SAP coincide with the analysis descriptions provided in the study protocol.

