Symptoms and Signs	Symptoms Subcategories	TOL-463 Vaginal Insert (N=X)					Placebo (N=X)					All Subjects (N=X)				
		Visit 0	Visit 1	Visit 2	Visit 3	Visit 4	Visit 0	Visit 1	Visit 2	Visit 3	Visit 4	Visit 0	Visit 1	Visit 2	Visit 3	Visit 4
Abnormal Vaginal Discharge	n	n	n	n	n	n	n	n	n	n	n	n	n	n	n	n
	No	x	x	x	x	x	x	x	x	x	x	x	x	x	x	x
	Yes, consistent with BV	x	x	x	x	x	x	x	x	x	x	x	x	x	x	x
	Yes, other	x	x	x	x	x	x	x	x	x	x	x	x	x	x	x
Vaginal Odor	n	n	n	n	n	n	n	n	n	n	n	n	n	n	n	n
	No	x	x	x	x	x	x	x	x	x	x	x	x	x	x	x
	Yes, consistent with BV	x	x	x	x	x	x	x	x	x	x	x	x	x	x	x
	Yes, other	x	x	x	x	x	x	x	x	x	x	x	x	x	x	x

Notes: N=Number of subjects in the mITT population in the specified group.

Subjects will be further excluded if no data is available at the specified timepoint, n=Number of subjects with available data for the specified category at the specified timepoint, and these counts are shown in the row of n, whereas the data shown in the rows of each response level in this table are percentages, where n is the denominator.

For post-enrollment visits, observations from early termination at an unscheduled visit will be summarized into the preceding scheduled visit. For Vaginal Discharge and Odor responses from the scheduled visit and the corresponding unscheduled early termination visit, count the subject in “Yes, consistent with BV” when at least one response was “Yes, consistent with BV”; count the subject in “Yes, other” when no response was in “Yes, consistent with BV” and at least one response was from “Yes, other”; count the subject in “No” when all responses were “No”.

Table 16: Summary of Proportion of Participants Reporting BV Symptoms – PP Population

Symptoms and Signs	Subcategories	TOL-463 Vaginal Insert (N=X)					Placebo (N=X)					All Subjects (N=X)				
		Visit 0	Visit 1	Visit 2	Visit 3	Visit 4	Visit 0	Visit 1	Visit 2	Visit 3	Visit 4	Visit 0	Visit 1	Visit 2	Visit 3	Visit 4
Abnormal Vaginal Discharge	n	n	n	n	n	n	n	n	n	n	n	n	n	n	n	n
	No	x	x	x	x	x	x	x	x	x	x	x	x	x	x	x
	Yes, consistent with BV	x	x	x	x	x	x	x	x	x	x	x	x	x	x	x
	Yes, other	x	x	x	x	x	x	x	x	x	x	x	x	x	x	x
Vaginal Odor	n	n	n	n	n	n	n	n	n	n	n	n	n	n	n	n
	No	x	x	x	x	x	x	x	x	x	x	x	x	x	x	x
	Yes, consistent with BV	x	x	x	x	x	x	x	x	x	x	x	x	x	x	x
	Yes, other	x	x	x	x	x	x	x	x	x	x	x	x	x	x	x

Notes: N=Number of subjects in the PP population in the specified group.

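### The BV-symptom secondary endpoint covers the whole follow-up period, but the SAP tabulates symptoms only visit by visit and never estimates the proportion of women with symptoms at any time

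*SAP*

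**What the plan says.** - **Objective and endpoint.** SAP 3.1.2 sets the objective as the incidence of vaginal symptoms over participation. SAP 3.2.2 defines the endpoint as "Proportion of participants reporting BV symptoms through the follow-up period".
- **Analysis.** SAP 4.5.1 says "the proportion of participants experiencing BV symptoms will be estimated overall, by symptom category, and by treatment group", with no mention of visits. SAP 8.2 gives the estimate "by symptom category, and by treatment group at each visit".
- **Tables.** Tables 15 (mITT) and 16 (PP) have columns for Visits 0 to 4 and no any-visit row. Their notes say: "Subjects will be further excluded if no data is available at the specified timepoint". SAP 6.5 likewise excludes missing values for secondary endpoints.
- **Exit.** Protocol 6.3.1 says: "Participants with a clinical diagnosis of BV recurrence will complete a satisfaction questionnaire and will be terminated from the study". Protocol 6.3.2 and 6.4 say the same for V3 and unscheduled visits. Recurrence means more than 2 Amsel criteria.
- **Source.** Protocol 10.5.4.2 takes symptoms "as assessed by the participant via the daily memory aid". Protocol 7.1.2 lets staff discard the "memory aid after documenting compliance". The SAP does not name the aid as the symptom source, and Listing 8 is organised by visit. SAP Section 15 nevertheless states: "The analyses described in this SAP coincide with the analysis descriptions provided in the study protocol".

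**The concern.** An incidence over participation needs one answer per woman: did she report BV symptoms at any time after baseline? The planned tables give several snapshots, each on a different set of women. After V2 the columns compare women still in follow-up, not the randomised groups. The report would therefore carry no estimate, interval or between-arm difference for a stated secondary endpoint.

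Some symptom reports also have no stated place in the tables. Table 15 folds in only unscheduled visits at which a woman terminates early. A woman who returns between visits with symptoms but two or fewer Amsel criteria continues in the study, and no rule says where that report goes. When a window holds several observations, SAP 4.5 keeps the one closest to the scheduled visit. Termination before V2 would fold into enrollment, yet the rule is limited to post-enrollment visits. Table 16 states no folding rule.

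**Working it through.** **1. Does any planned output give the cumulative figure?** SAP 8.2 and 4.5.1 both use the word overall, but SAP 6.1 uses it for the All Subjects column, and that is all the shells implement. Listing 8 shows individual data without a summary. By contrast, endpoints 4 and 5 (related AEs, culture-confirmed VVC), which run to the final study visit, each get one per-woman proportion with a Wilson interval and a Newcombe difference (SAP 9.3 and 9.8, Tables 27 and 36). SAP 6.1 promises Wilson intervals for efficacy proportions and differences, but Tables 15 and 16 show none.

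**2. Inputs for an illustration.** SAP Section 5 assumes 40% recurrence on placebo and 20% on TOL-463, with 200 evaluable women. Its power figure, which concerns the primary endpoint, reproduces: (0.20 − 1.96 × √(2 × 0.3 × 0.7/100)) / √((0.24 + 0.16)/100) = 1.154, or 87.6% power, consistent with at least 85%. The documents state no figure for symptoms. Assumed here: the timing split over V2/V3/V4 (the same in both arms), the share of recurrences that are symptomatic, no symptoms in other women and no other dropout.

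**3. V4 column under the Table 15 rule.** Per 100 women randomised, V4 percentage = symptomatic recurrences at V4 / (100 − recurrences at V2 and V3). With every recurrence symptomatic:

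| Split V2/V3/V4 | Placebo V4 | TOL-463 V4 | V4 difference (points) | Cumulative difference (points) |
|---|---|---|---|---|
| 70/20/10 | 4/64 = 6.3% | 2/82 = 2.4% | 3.8 | 20 |
| 50/30/20 | 8/68 = 11.8% | 4/84 = 4.8% | 7.0 | 20 |
| equal | 13.33/73.33 = 18.2% | 6.67/86.67 = 7.7% | 10.5 | 20 |
| 20/30/50 | 20/80 = 25.0% | 10/90 = 11.1% | 13.9 | 20 |

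Differences come from unrounded percentages. If half of recurrences are symptomatic, every figure halves: 1.9 to 6.9 points at V4 against 10 cumulatively.

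**4. Can the columns be summed?** No. With the equal split, the placebo columns are 13.3%, 15.4% and 18.2%, which add to 46.9% against a true 40%, because the denominator shrinks. Repeat counting adds to this. Suppose 5% of women without recurrence also report symptoms at each visit, independently. Placebo counts are then 13.33 + 0.05 × 86.67 = 17.67, 13.33 + 0.05 × 73.33 = 17.00 and 13.33 + 0.05 × 60 = 16.33. They total 51.0, but only 100 − 60 × 0.95³ = 48.6 women are ever symptomatic.

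**5. Does restricting to women still in follow-up shrink the V4 difference?** In the equal split, V4 events over all randomised women are 13.3% vs 6.7%, a difference of 6.7 points. Restricting to women still in follow-up gives 10.5. The restriction widens the V4 difference. The distance to 20 points reflects one interval against three.

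**The case against.** The best defence is that this is a descriptive secondary endpoint without a hypothesis test, in a Phase II trial that closed early, so the primary result and type I error are untouched. The phrase about the follow-up period is not decisive either: SAP 3.2.2 also applies it to satisfaction, which is collected once, at exit or V4. Symptoms at exit are not discarded. A woman with recurrence counts at her diagnosis visit, Table 15 folds in unscheduled early terminations, and Listing 8 shows every report by visit. If symptoms matched recurrence exactly, Table 6 and Figure 3 would already carry the contrast.

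Most of this limits the importance of the point without removing it. The objective's word incidence supports a cumulative reading, as does the handling of endpoints 4 and 5. Symptoms and recurrence are different things, so the primary table cannot stand in for this endpoint.

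Three stronger readings are tempting but unsupported:

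- **Conditioning on remaining in the study attenuates the effect.** Step 5 shows the reverse at V4.
- **Symptomatic women drop out of every later column.** Exit depends on Amsel criteria. Symptomatic women below the threshold stay, and women with recurrence but no symptoms leave.
- **All symptoms between visits are lost.** Women with symptoms are asked to return, and staff review the aid and assess symptoms at each follow-up visit. What the SAP drops is the aid as the analysis source. The documents do not show whether its symptom entries were captured.

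**Conclusion.** The point holds as a gap between endpoint and analysis: the plan as written does not estimate secondary endpoint 2, and its by-visit tables cannot supply the figure. The change of symptom source is a real and undeclared departure from the protocol. Under the assumptions in step 2, the V4 column would show roughly 4 to 14 points where the cumulative difference is 20, or 2 to 7 where it is 10. These ranges illustrate how far a single visit can differ from the endpoint; they are not an estimate of bias. They depend on timing and symptomatic share, which the documents do not give. The change should be made, but nothing here bears on the primary analysis.

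**What to change.** - **Tables 15 and 16.** Add a row per arm for any post-baseline report of discharge or odor consistent with BV, at any scheduled, unscheduled or early-termination visit through V4, with Wilson intervals and a Newcombe difference. Keep the by-visit columns as descriptive.
- **Denominator.** State it, with a rule for incomplete follow-up. One option is all women with a post-baseline assessment, plus a sensitivity analysis for symptom-free women who left early. Without such a rule, a woman seen only at V2 without symptoms counts as never symptomatic.
- **SAP Section 15.** Record that the source changed from the daily memory aid to visit assessments. Include aid entries only if they were already captured; after early closure, new data entry is probably not possible.

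The cost is SAP wording and one extra row in two tables, from visit data the protocol already collects. The drawback is that symptom assessment at unscheduled visits is at the site investigator's discretion (Protocol 6.4), so ascertainment there may be uneven.

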8.3. Exploratory Efficacy Analyses

The exploratory endpoint is to evaluate the performance of the BD Max Vaginal Panel in characterizing clinical and microbiologic outcomes of the intervention. Amsel criteria of 3 or more will be considered as the gold standard for the RBV clinical outcome. Nugent score of ≥ 7 will be considered as the gold standard for the microbiologic BV outcome. For BD Max Vaginal Panel testing result of BV compared to clinical and microbiologic outcomes, we will present sensitivity, specificity, positive predictive value (PPV), and negative predictive value (NPV) and corresponding 95% Wilson CI by study visit ([Table 19](#)). The individual BD Max BV result will also be listed in [Listing 6](#).

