## **7.2      Laboratory Evaluations**

### **7.2.1      Clinical Laboratory Evaluations**

At the screening visit, V0, diagnostic laboratory tests for determination of *C. trachomatis*, *N. gonorrhoeae*, and *T. vaginalis* (NAATs) will be performed locally. Vaginal Gram stain Nugent scoring for microbiologic confirmation of clinical findings will be conducted in the Central Laboratory. BD Max baseline testing will be conducted at a certified laboratory. Instructions for obtaining vaginal swab specimens for these assessments are outlined in the protocol-specific MOP.

A urine pregnancy test will be performed at all visits on all participants of childbearing potential. Screening and enrollment visit results must be negative and known prior to randomization on V1.

---

At all scheduled study visits a BD Max test will be conducted at a certified laboratory. At the enrollment and follow-up visits, vaginal Gram stain Nugent scoring for microbiologic confirmation of clinical findings will be conducted in the Central Laboratory. At the follow-up visits participants with clinically diagnosed VVC will have a confirmatory culture for vaginal *Candida* with speciation performed locally.

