3.2. Endpoints

3.2.1. Primary Endpoint

Among participants with a history of BV and negative (<=2 Amsel criteria and asymptomatic) at enrollment, the proportion of participants with recurrent BV by V4 as defined by clinical cure [Study day 85-91].

Recurrence of BV at each follow-up visit is defined as > 2 of the following Amsel criteria:

- a. Positive KOH whiff test
- b. Homogeneous discharge characteristic of BV
- c. Clue cells $\geq 20\%$ of vaginal squamous epithelial cells
- d. Vaginal pH > 4.5

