Sensitivity = $TP/(TP + FN) = (\text{Number of true positives})/(\text{Number of sick individuals in the population})$

Specificity = $TN/(TN + FP) = (\text{Number of true negatives})/(\text{Number of all well individuals in the population})$

PPV = $TP/(TP+FP) = (\text{Number of true positives})/(\text{Number of positive calls})$

NPV = $TN/(TN+FN) = (\text{Number of true negatives})/(\text{Number of negative calls})$

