4. INVESTIGATIONAL PLAN

4.1. Overall Study Design and Plan

This is a Phase II randomized, double-blind, placebo-controlled study screening approximately 600 adult females 18-55 years of age to enroll approximately 250 participants in total (125 per arm) to achieve 200 evaluable participants at the test of cure (TOC) visit. The study is designed to determine the clinical efficacy of an investigational product (IP), TOL-463 Insert, manufactured by Toltec Pharmaceuticals, in suppressing RBV when administered to women who have a history of RBV and have been successfully cleared of their current BV infection using oral metronidazole, 500 mg twice a day for 7 days or another CDC-recommended BV treatment.

Participants who consent to screening will have baseline clinical information collected at Visit 0, screening (Day -15 to -8), (V0). This information will consist of demographics, current vaginal symptoms, medical and sexual history, concomitant medications, and clinical and laboratory findings. Participants will undergo a pelvic examination and have vaginal specimens collected for confirmation of BV and for diagnostic testing for common STIs (*C. trachomatis*, *N. gonorrhoeae*, and *T. vaginalis*). Women with a clinical diagnosis of BV who meet all other screening Inclusion/Exclusion criteria will be treated with oral metronidazole, 500 mg twice a day for 7 days, or another CDC-recommended BV treatment, and scheduled for a Visit 1, enrollment, (V1) in 8 to 15 days. At the enrollment visit, women who test negative for BV, defined as ≤ 2 of 4 Amsel criteria and absence of symptoms of BV (absence of homogenous discharge and odor), will be offered to review and sign the Enrollment consent. Women who consent and qualify will be enrolled and randomized (1:1) to one of two groups (TOL-463 Insert or placebo). IP will be self-administered vaginally, twice-weekly for 12 weeks. Follow-up clinic visits will occur at Visit 2 (V2), Visit 3 (V3), and Visit 4 (V4). For women with cleared BV at enrollment, the primary endpoint will be clinical failure, recurrence of BV by V4.

[figure not shown]
Safety will be measured by participant report, targeted physical examination, and pelvic examination. All AEs will be collected through V4. Safety oversight will be provided by a Data and Safety Monitoring Board (DSMB).

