	Very inconvenient	x	x	x
	Inconvenient	x	x	x
	Somewhat convenient	x	x	x
	Convenient	x	x	x
	Very convenient	x	x	x

Satisfaction Questions	Responses	TOL-463 Vaginal Insert (N=X)	Placebo (N=X)	All Subjects (N=X)
	Extremely convenient	x	x	x
Overall Satisfaction	n	n	n	n
	Extremely dissatisfied	x	x	x
	Very dissatisfied	x	x	x
	Dissatisfied	x	x	x
	Somewhat satisfied	x	x	x
	Satisfied	x	x	x
	Very satisfied	x	x	x
	Extremely satisfied	x	x	x
Would Use Again	n	n	n	n
	Yes	x	x	x

Notes: N=Number of subjects in the PP population in the specified group.

Subjects will be further excluded if no data is available, n=Number of subjects with available data for the specified question, and these counts are shown in the row of n, whereas the data shown in the rows of each response level in this table are percentages, where n is the denominator.

The questions are structured as “How satisfied or dissatisfied are you with …”, where the following part of the question is shown in the table.

Table 19: Performance of BD Max Vaginal Panel

Study Visit	Condition	N	Prevalence	BD Max Proportion of Positives	Sensitivity (%) (95% CI)	Specificity (%) (95% CI)	PPV ^a (%) (95% CI)	NPV ^b (%) (95% CI)
Visit 1 - Enrollment	Clinical BV	x	0.xx	0.xx	x (0.xx, 0.xx)	x (0.xx, 0.xx)	x (0.xx, 0.xx)	x (0.xx, 0.xx)
	Microbiological BV	x	0.xx	0.xx	x (0.xx, 0.xx)	x (0.xx, 0.xx)	x (0.xx, 0.xx)	x (0.xx, 0.xx)
Visit 2 – Month 2	Clinical BV	x	0.xx	0.xx	x (0.xx, 0.xx)	x (0.xx, 0.xx)	x (0.xx, 0.xx)	x (0.xx, 0.xx)
	Microbiological BV	x	0.xx	0.xx	x (0.xx, 0.xx)	x (0.xx, 0.xx)	x (0.xx, 0.xx)	x (0.xx, 0.xx)
Visit 3 – Month 3	Clinical BV	x	0.xx	0.xx	x (0.xx, 0.xx)	x (0.xx, 0.xx)	x (0.xx, 0.xx)	x (0.xx, 0.xx)
	Microbiological BV	x	0.xx	0.xx	x (0.xx, 0.xx)	x (0.xx, 0.xx)	x (0.xx, 0.xx)	x (0.xx, 0.xx)
Visit 4 – Month 4	Clinical BV	x	0.xx	0.xx	x (0.xx, 0.xx)	x (0.xx, 0.xx)	x (0.xx, 0.xx)	x (0.xx, 0.xx)
	Microbiological BV	x	0.xx	0.xx	x (0.xx, 0.xx)	x (0.xx, 0.xx)	x (0.xx, 0.xx)	x (0.xx, 0.xx)

Notes: N is number of subjects with available BV results from both the standard diagnosis method (clinical diagnosis or microbiological diagnosis as specified by the row) and the BD Max Vaginal Panel testing method.

95% CI Wilson confidence interval is provided in this table.

^a Positive Predictive Value

^b Negative Predictive Value

Table 20: Original Clinical BV Diagnosis and the Nugent Score Assessment at the Screening Visit - All Enrolled Subjects

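### Table 19's clinical-BV row at Visit 1 can yield only specificity, because eligibility leaves no clinical positives; a pooled V2-V4 row and a V0 sensitivity-only row would use the scheduled BD Max tests better

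*SAP*

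**What the plan says.** SAP 8.3 sets two reference standards for the BD Max Vaginal Panel: a Nugent score of 7 or more for microbiologic BV, and for clinical BV, "Amsel criteria of 3 or more will be considered as the gold standard for the RBV clinical outcome". It then says "we will present sensitivity, specificity, positive predictive value (PPV), and negative predictive value (NPV) and corresponding 95% Wilson CI by study visit". SAP 3.3 defines the measures; the denominator of sensitivity is TP + FN, described as "Number of sick individuals in the population".

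The Table 19 shell has a clinical and a microbiological row for each of four visits, starting at "Visit 1 - Enrollment" and ending at Visit 4. It has no Visit 0 row. It names no analysis population; its note says "N is number of subjects with available BV results from both the standard diagnosis method".

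Four other parts of the plan bear on this:

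- **Visit 1 eligibility.** SAP 4.1 admits "women who test negative for BV, defined as ≤ 2 of 4 Amsel criteria and absence of symptoms of BV". SAP 4.3 allows no exemptions.
- **Visit 0 eligibility.** SAP 4.3.1.1 requires 3 or more Amsel criteria at screening.
- **Testing.** Protocol 7.2.1 says "At all scheduled study visits a BD Max test will be conducted at a certified laboratory", and the schedule of events marks it at Visit 0. At Visit 1 the additional swabs are taken only from women who are enrolled and randomized (Protocol 6.2; SAP Table 1, footnote 6).
- **End of participation.** A woman leaves the study once clinical BV recurs (Protocol 5, 6.3.1, 6.3.2 and 6.4).

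**The concern.** The entry rule and the reference standard use the same Amsel cut-off from opposite sides. A woman with 3 or more criteria at Visit 1 is not enrolled and gives no Visit 1 BD Max swab, so she cannot enter the table. The Visit 1 clinical row therefore asks for accuracy measures in a group that contains only reference negatives.

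The shell also reports sensitivity for recurrence visit by visit, with no pooled row, so each estimate rests on few positives. Visit 0, where eligibility makes every enrolled woman a clinical positive and where BD Max is scheduled, gets no row.

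At stake is whether the one table serving the exploratory objective can be filled in and read correctly. A PPV of 0% and an NPV of 100% at Visit 1 could be taken for properties of the assay when they are consequences of the entry rule.

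**Working it through.** The documents give no expected figure for Table 19, so there is no stated result to reproduce.

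**1. Visit 1, clinical row.** Under the eligibility rules TP = 0 and FN = 0. With N women tested and FP of them BD Max positive:

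- Sensitivity = TP/(TP + FN) = 0/0, so there is no estimate and no interval.
- PPV = TP/(TP + FP) = 0/FP, which is 0% if FP > 0 and undefined if FP = 0.
- NPV = TN/(TN + FN) = TN/TN = 100% whatever the assay does.
- Specificity = TN/(TN + FP) = (N − FP)/N, which is informative.

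Example with N = 200 and an assumed 10% BD Max positive (FP = 20):

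- Specificity is 180/200 = 90% (Wilson 95% CI 85.1-93.4%).
- PPV is 0/20, with a formal interval of 0-16.1%.
- NPV is 180/180, with a formal interval of 97.9-100%.

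The last two intervals look like findings but carry no information about the test.

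**2. Visit 1, microbiological row.** Nugent score is not an enrollment criterion, so both Nugent positives and Nugent negatives can occur. All four measures can be estimated.

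**3. Follow-up visits.** Inputs from SAP 5 are 200 evaluable women and recurrence of 40% and 20% with 1:1 allocation.

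- Average recurrence is (40% + 20%)/2 = 30%.
- Expected clinical positives over V2-V4 are 0.30 × 200 = 60.
- An even split over three visits, which is my assumption, gives 60/3 = 20 per visit.

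The Wilson interval has centre (p + z²/2n)/(1 + z²/n) and half-width z√[p(1 − p)/n + z²/4n²]/(1 + z²/n), with z = 1.96. For p = 0.90 (assumed) and n = 20, the centre is 0.996/1.192 = 0.836 and the half-width is 0.163/1.192 = 0.137, giving 0.699 to 0.972.

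**4. Visit 0, clinical row.** Every enrolled woman is reference-positive, so sensitivity is TP/N. Specificity is 0/0, PPV is fixed at 100% and NPV at 0%. Only sensitivity is informative.

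**5. Comparison on one base.** Sensitivity is assumed to be 90% throughout. SAP 5 reports early closure without giving the number enrolled, so the last column repeats the calculation for an assumed 100 women.

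| Source of clinical positives | 200 women: n, 95% CI | 100 women (assumed): n, 95% CI |
|---|---|---|
| One follow-up visit | 20, 69.9-97.2% | 10, 59.6-98.2% |
| V2-V4 pooled | 60, 79.9-95.3% | 30, 74.4-96.5% |
| Visit 0 | 200, 85.1-93.4% | 100, 82.6-94.5% |

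**6. Repeated women in a pooled row.** Participation ends at clinical recurrence, and SAP 6.1 counts repeat participants once outside the safety tables. Each woman therefore supplies at most one clinical positive, and the ordinary Wilson interval serves for pooled clinical sensitivity. She may supply up to three clinical negatives and more than one BD Max positive or negative. A Nugent score of 7 or more does not end participation. Pooled specificity, PPV, NPV and all pooled Nugent measures therefore contain correlated observations.

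**The case against.** **Visit 0 lies outside the objective.** The exploratory endpoint concerns outcomes of the intervention, and the clinical standard is attached to recurrence. The primary endpoint likewise takes women negative "at enrollment, the proportion of participants with recurrent BV by V4". The Amsel and Nugent by-visit tables (Tables 11, 12 and 14) also start at Visit 1, and Listing 6 keeps the Visit 0 BD Max results. This stands in part. Visit 1 also precedes study treatment and is included, and Table 15 does show Visit 0, so the convention is not uniform. But leaving out Visit 0 is a choice the plan can defend; it is not an error.

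**Visit 0 does not measure recurrence detection.** A reader might infer from the narrower Visit 0 interval that adding that row would cure the imprecision at follow-up. The documents do not support this. Visit 0 describes untreated, presenting BV in women selected for 3 or more criteria; the follow-up rows describe recurrence during suppression. Only pooling V2-V4 adds precision for the latter. A Visit 0 Nugent row would have a similar limit, since its Nugent negatives would all be Amsel-positive women.

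**The consequence is small.** The shell has a prevalence column, so zero clinical prevalence at Visit 1 would be visible and a programmer would probably print the sensitivity cell as not estimable. This is fair for sensitivity. It is less so for PPV and NPV, which would print as ordinary percentages.

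**A woman enrolled in error could be a clinical positive.** True, but one or two such cases would not give a usable sensitivity estimate.

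**Conclusion.** The concern holds for the Visit 1 clinical row. By eligibility, sensitivity there cannot be computed, PPV is 0% or undefined, and NPV is 100%. This needs no assumption beyond adherence to the entry criteria. Specificity in that row, and the whole Visit 1 microbiological row, remain valid, so it would be wrong to conclude that Visit 1 should be dropped or that the BD Max analysis fails.

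The rest is an opportunity for improvement. On planned numbers, pooling V2-V4 narrows the interval for clinical sensitivity from 69.9-97.2% to 79.9-95.3%. Those figures assume 30% average recurrence in 200 women, an even split over visits, 90% sensitivity and a paired BD Max result for every recurrence. The last may fail: BD Max is not scheduled at unscheduled visits, and although it is scheduled at early termination, Table 19 has no rule assigning those results to a visit. Early closure should make the real counts smaller.

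The table is exploratory. The primary and secondary conclusions are unaffected.

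**What to change.** In the Table 19 shell:

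1. **Visit 1, clinical row.** Print sensitivity as not estimable, and PPV and NPV as fixed by design, with a footnote citing the entry criterion. Keep specificity. Leave the microbiological row as it is.
2. **Pooled V2-V4 rows.** Add them for both reference standards. Use the Wilson interval for clinical sensitivity. For clinical specificity, PPV and NPV, and for all Nugent measures, use intervals that allow for repeated women, such as a bootstrap that resamples women or a robust variance clustered on woman. State how early-termination results enter.
3. **Visit 0, clinical row.** Report sensitivity only, labelled as presenting (pre-induction) BV and as a complement to the recurrence rows. If a Visit 0 Nugent row is added, footnote that it covers only women selected for 3 or more Amsel criteria.

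The cost is a revised shell, footnotes and modest programming. The protocol already schedules every test involved, so no new visit, sample or assay is needed. The documents show that testing is planned, not that it was completed, so availability of paired results should be checked first.
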